9.9. Limitations of the research methods

Information bias

- Outcome misclassification is possible as the records of diagnoses reported in the HIRA database may be different from their actual diagnoses recorded in the hospital's electronic medical records.
- To minimize any bias arising from exposure misclassification, analyses will be repeated by using a 15 and 60-day grace period definition for non-overlapping successive prescriptions.

Selection bias

[figure not shown]
- By using the nationwide HIRA database that encompasses the entire Korean population of 50 million, this study is unlikely to miss out any patients with VTE in South Korea.

Confounding bias

- Owing to the nature of observational studies, residual confounding from unmeasured or unaccounted confounders may be present.
- Nevertheless, to minimize confounding bias, we will apply various PS approaches, with the IPTW approach applied as our main analysis.

External validity of study design

PFIZER CONFIDENTIAL

- Our study results will achieve generalizability by using the nationwide HIRA database.

Analysis limitations

- Potential incompleteness of information on potential confounders such as laboratory data are unavailable for assessment due to inherent limitations of the HIRA database as its primary purpose is for administrative means.
- Sensitivity analysis using the E-value will be conducted to quantify the impact of residual confounding from unmeasured or unaccounted confounders on the risk estimates for the association between apixaban use and risk of VTE recurrence and bleeding events.

Limitations due to missing and/or incomplete data

- HIRA data are released for research only after thorough internal review, this would not be applicable to HIRA data.

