Diabetes without chronic complication	1	E10.0, E10.1, E10.6, E10.8, E10.9, E11.0, E11.1, E11.6, E11.8, E11.9, E12.0, E12.1, E12.6, E12.8, E12.9, E13.0, E13.1, E13.6, E13.8, E13.9, E14.0, E14.1, E14.6, E14.8, E14.9
Mild liver disease	1	B18, K70.0-K70.3, K70.9, K71.3-K71.5, K71.7, K73, K74, K76.0, K76.2-K76.4, K76.8, K76.9, Z94.4
Myocardial infarction	1	I21, I22, I25.2
Peripheral vascular disease	1	I70, I71, I73.1, I73.8, I73.9, I77.1, I79.0, I79.2, K55.1, K55.8, K55.9, Z95.8, Z95.9
Peptic ulcer disease	1	K25-K28
Rheumatologic disease	1	M05, M06, M32–M34, M31.5, M35.1, M35.3, M36.0
Diabetes with chronic complication	2	E10.2–E10.5, E10.7, E11.2–E11.5, E11.7, E12.2–E12.5, E12.7, E13.2–E13.5, E13.7, E14.2–E14.5, E14.7
Hemiplegia or paraplegia	2	G04.1, G11.4, G80.1, G80.2, G81, G82, G83.0-G83.4, G83.9
Any malignancy, including leukemia and lymphoma	2	C00–C26, C30–C34, C37–C41, C43, C45–C58, C60–C76, C81–C85, C88, C90–C97
Renal disease	2	I12.0, I13.1, N03.2-N03.7, N05.2–N05.7, N18, N19, N25.0, Z49.0–Z49.2, Z94.0, Z99.2
Moderate or severe liver disease	3	I85.0, I85.9, I86.4, I98.2, K70.4, K71.1, K72.1, K72.9, K76.5, K76.6, K76.7
AIDS/HIV	6	B20–B22, B24
Metastatic solid tumor	6	C77-C80

List of HAS-BLED	Score	ICD-10 codes

Hypertension	1	I10-I15
Abnormal renal function	1	N18.3, N18.4, N18.5, N19, Z94.0, Z99.2
Abnormal liver function	1	B15-B19, C22, D68.4, I98.2, I98.3, K70-K77, Z94.4
Stroke	1	I63, I69.3, G45.9
Bleeding history	1	Intracranial and GI: I60, I61, I62, I69.0, I69.1, I69.2, S06.4, S06.5, S06.6, S06.8, I85.0, I98.3, K22.11, K22.6, K22.8, K25.0, K25.2, K25.4, K25.6, K26.0, K26.2, K26.4, K26.6, K27.0, K27.2, K27.4, K27.6, K28.0, K28.2, K28.4, K28.6, K29.0, K31.81, K55.21, K62.5, K92.0, K92.1, K92.2 Other sites*: D62, H44.8, H35.72, H35.6, H31.3, H21.0, H11.3, H05.2, H47.0, H43.1, I31.2, N02.0-N02.9, N42.1, N83.1, N85.7, N92.0, N92.3, N93.0, N93.8, N93.9, M25.0, R23.3, R04.0, R04.1, R04.2, R04.8, R04.9, T79.2, T81.0, N95.0, R31.0, R31.1, R31.8, R58, T45.5, Y44.2, D68.3
Labile INR	1	Not applicable
Elderly > 65 years	1	
Drugs or alcohol concomitantly	1	Antiplatelet agents, NSAIDs
	1	Alcoholism: E24.4, F10, G31.2, G62.1, G72.1, I42.6, K29.2, K70, K86.0, O35.4, R78.0, T51.0, X45, X65, Y15, Y90, Y91, Z71.4, Z72.1

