*Blood transfusion (Korean Procedure Codes: X1001, X1002, X2011, X2012, X2021, X2022, X2031, X2032, X2041, X2042, X2051, X2052, X2061, X2062, X2071, X2072, X2081, X2082, X2091, X2092, X2101, X2102, X2111, X2112, X2121, X2122, X2131, X2132, X2141, X2142, X3010) will also be used to define other site bleeding history.

- Initial presentation of VTE
 - DVT (I80.2, I80.3)

- PE (I26.0, I26.9)
- Both DVT and PE
- Comorbidities (ICD-10 diagnostic code) will be measured within the 6-month period prior to the index date.
 - Antiphospholipid syndrome (D68.6, I82.9): As diagnosis of antiphospholipid syndrome is usually made after VTE diagnosis with subsequent diagnostic procedures, its presence will be evaluated within the 6-month period after the index date.
 - Asthma (J45)
 - Cancer (C00-C97): History of cancer (non-active) will be evaluated within a lifetime prior to the index date.
 - Chronic obstructive pulmonary disease (COPD; J40-J44)
 - Chronic kidney disease (N18, N19)
 - Chronic liver disease (B18, B19, K70-K77)
 - Diabetes mellitus (E10-E14)
 - Fracture (S22, S32, S42, S52, S62, S72, S82, S92, T10, T12)
 - Heart failure (I50)
 - Hyperlipidemia (E78)
 - Hypertension (I10-I15)
 - Ischemic heart disease (I24, I25)
 - Myocardial infarction (I21)
 - Stroke (I60-I64, I69, G45)
 - Trauma (T79, T98, V01–V99, W11–W17, W50–W52, W64, X34–X39, Y01–Y04, Y30–Y32)
- Previous use of medications (WHO-ATC code) will be measured within the 6-month period prior to the index date.
 - Corticosteroids (H02)
 - Nonsteroidal anti-inflammatory drugs (NSAIDs; M01A)
 - Angiotensin-converting enzyme (ACE) inhibitors (C09A, C09B)

- Angiotensin II receptor blockers (ARBs; C09C, C09D)
- Antiplatelet agents (aspirin [N02BA01], aspirin/dipyridamole [B01AC30], abciximab [B01AC13], beraprost [B01AC19], cilostazol [B01AC23], clopidogrel [B01AC04], iloprost [B01AC11], indobufen [B01AC10], limaprost [C04AX], ozagrel [R03DX], prasugrel [B01AC22], sarpogrelate [B01AC], ticagrelor [B01AC24], ticlopidine [B01AC05], tirofiban [B01AC17], treprostinal [B01AC21], triflusal [B01AC18])
- Azole antifungal agents (fluconazole [J02AC01], itraconazole [J02AC02], voriconazole [J02AC03], posaconazole [J02AC04])
- β -blockers (C07)
- Calcium-channel blockers (C08)
- Selective serotonin reuptake inhibitors (SSRIs; N06AB)
- Proton pump inhibitors (PPIs; A02BC)
- Diuretics (C03)
- Thiazides (C03A)
- Vasodilators (C01D, C04A)
- Estrogens (G03C)
- Cyclooxygenase (COX)-2 inhibitors (M01AH)

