- Number of outpatient visits within the 6-month period prior to the index date.

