- In the NOAC-based group, all analyses will be repeated stratified by each individual NOAC class (e.g, apixaban, dabigatran, rivaroxaban, edoxaban) to

PFIZER CONFIDENTIAL

identify the difference in baseline characteristics and treatment patterns between each NOAC class.

- To identify potential reasons for treatment change, clinical events preceding the first treatment change (major bleeding, thromboembolism diagnosis, complications of VTE, major surgery, active cancer, a new diagnosis of CKD or AKI, a new diagnosis of liver disease or abnormal liver function) will be measured within 30 days prior to the first date of treatment change. Patients can contribute with multiple events.
- All analyses of treatment patterns will be presented stratified according to the index anticoagulant treatment, and not overall or per drug class.

Phase II of the study (comparative)

Propensity score analysis

- To balance and adjust for any potential differences in baseline sociodemographic and clinical characteristics between treatment groups, propensity score (PS) methods will be implemented.
 - A logistic regression model will be used to estimate the predicted probability (propensity) of initiating each NOAC compared with warfarin given baseline covariates mentioned above. By using the estimated PS, we will apply the PS based on the inverse probability of treatment weights (IPTW), where the treatment group of interest will be given a weight of 1/PS, and the comparator group will be given a weight of 1/(1-PS) [4, 5]. The most extreme 1% of PS values (IPTW with trimming) will be excluded to improve comparability between exposure groups.

Main Analysis

- Sociodemographic and clinical characteristics will be summarized with means (STD) or median (IQR) for continuous variables and with count (proportions) for categorical variables for the two treatment comparisons of: apixaban vs warfarin, rivaroxaban vs warfarin, edoxaban vs warfarin and dabigatran vs warfarin (and NOAC vs NOAC, if scientifically feasible).
 - Differences in baseline covariates between users of different OACs will be assessed using the SD where the absolute SD <0.1 will be considered as well balanced.
- The incidence rate of major bleeding overall and by site will be presented as the total number of events per 1,000 person-years, with its 95% CIs estimated using the Poisson distribution.

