- The risk of major bleeding according to the treatment of interest will be investigated in time-to-event analyses using standard Kaplan-Meier methods.

- Cox proportional hazards model will be used to compare the safety outcome between users of different OACs, weighted on the estimated PS according to the IPTW approach.
 - Proportionality assumption will be tested by use of Schoenfeld residuals.

Subgroup Analysis

- The potential heterogeneity of treatment effects in selected subgroups of patients with VTE will be examined for the major bleeding as follows:
 - Aged <65 years vs. aged \geq 65 years
 - Females vs. males
 - Setting of VTE diagnosis (inpatient vs. outpatient)
 - Type of VTE (DVT without PE [ICD-10: I80.2, I80.3] vs. PE with or without DVT [I26.0, I26.9])
 - Major orthopedic surgery-provoked VTE
 - Major orthopedic surgery-provoked VTE is defined as an event preceded by knee arthroplasty, hip arthroplasty, or hip fracture surgery (National Procedure Codes: N0305, N0601, N0611, N0641, N0711, N2070, N0715, N2710, N0731, N0981, N0991, N1711, N3710, N1721, N3720, N1715, N4710, N1725, N4720, N2072, N2077, N2712, N2717, N3712, N3717, N3722, N3727, N4712, N4717, N4722 or N4727) within 3 months period prior to index date
 - With vs. without CKD stage 3 or 4 (N18.3, N18.4)
- P-for-interaction value <0.05 will be used to denote a significant difference between the two groups.

Sensitivity Analysis

- Vary the definition of treatment interruption/discontinuation to 15 and 60 days (allowing for varying non-adherence) to assess the effect this had on study outcomes.
- Four other approaches involving PS will be applied to determine the robustness of our study findings. First, we will vary the extreme value of PS in trimming process (most extreme 5%, and 10% will be excluded). Second, we will include the estimated PS, in addition to other covariates, into our multivariable Cox proportional hazards regression model. Third, we will stratify on the estimated PS in deciles. Last, we will apply another weighting approach, standardized mortality ratio weights, with the weights given as follows: 1 for the treatment group of interest and PS/(1 – PS) for the comparator group.[4]

- Exclude patients with a history of bleeding during the 6-month pre-index-date period in Phase II comparative analysis to evaluate the robustness of findings with respect to changes in underlying risk of patients

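### The propensity score has no term for CKD stage 5 or dialysis, so confounding by severe renal disease may remain and would not show in balance Tables 13-16

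*SAP*

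**What the plan says.** SAP 10 fits a logistic PS for each NOAC against warfarin, "given baseline covariates mentioned above". These are the potential confounders in SAP 8.4, repeated in Protocol 9.3. Three of them carry renal information:

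- The comorbidity flag "Chronic kidney disease (N18, N19", which covers every N18 stage.
- The CCI total, which adds 2 points for any code in its renal list. That list includes N18, N19, Z49.0-Z49.2, Z94.0 and Z99.2.
- The HAS-BLED total, which adds 1 point for any of "N18.3, N18.4, N18.5, N19, Z94.0, Z99.2".

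No exclusion criterion in SAP 8.3.2 removes stage 5 or dialysis. Tables 13-16 show CKD as one row. SAP 10 calls a covariate balanced when its absolute standardized difference (SD, in the plan's usage) is below 0.1. The one stage-specific analysis is the subgroup "With vs. without CKD stage 3 or 4 (N18.3, N18.4").

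**The concern.** Inverse probability weighting balances what is in the PS model. If that model does not separate moderate from end-stage renal disease, weighting can equalise the proportion with CKD while leaving its severity different between arms. NOAC users with moderate CKD are then weighted up to represent warfarin users with stage 5 disease.

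The plan itself treats renal disease as a bleeding-risk item (HAS-BLED), as a confounder, as a possible reason for changing treatment and as a possible effect modifier by stage. Residual imbalance in the most severe group therefore bears on the Phase II primary result. The balance diagnostic could not reveal it, because the tables have no row in which it would appear.

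**Working it through.** **1. Coding check.** Each code combination is run through the SAP 8.4 definitions:

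| Codes in the 6-month window | CKD flag | CCI renal points | HAS-BLED renal point |
|---|---|---|---|
| N18.1, N18.2 or N18.9 | 1 | 2 | 0 |
| N18.3 | 1 | 2 | 1 |
| N18.4 | 1 | 2 | 1 |
| N18.5 | 1 | 2 | 1 |
| N18.5 + Z99.2 | 1 | 2 | 1 |
| N18.9 + Z49 | 1 | 2 | 0 |
| Z99.2 alone | 0 | 2 | 1 |
| Z49 alone | 0 | 2 | 0 |

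Rows N18.3 to N18.5 + Z99.2 are identical. The last two rows show dialysis patients whom the flag counts as having no CKD. The CCI and HAS-BLED values enter as totals, so their renal part is not separately visible to the model.

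**2. What flag-only weighting leaves.** The documents give no renal prevalence, prescribing split or stage-specific risk, so these inputs are assumptions:

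- severe disease (stage 5 or dialysis): sW = 2-5% of warfarin users, sN = 0.2-0.5% of NOAC users;
- hazard R = 3-4 times that of patients without CKD;
- moderate CKD: 4% in both arms, hazard 1.5 times;
- no true drug effect.

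The NOAC share a is the plan's: 39.3% for apixaban and 69.1% for rivaroxaban.

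Let cW = sW + 4% and cN = sN + 4%. Weighting on the flag sets CKD prevalence in both arms to c = a·cN + (1 - a)·cW. The severe share within CKD does not change, so weighted severe prevalence is e = c·s/(s + 4%) in each arm. The mean hazard is (1 - c) + 1.5(c - e) + R·e. The bias factor is the NOAC mean divided by the warfarin mean.

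Worked case, 5% vs 0.5%, R = 4, a = 0.691:

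- c = 0.691 × 0.045 + 0.309 × 0.09 = 0.0589.
- Warfarin: e = 0.0589 × 5/9 = 0.0327, mean hazard 1.111.
- NOAC: e = 0.0589 × 0.5/4.5 = 0.0065, mean hazard 1.046.
- Factor = 1.046/1.111 = 0.941.
- SD = (0.0327 - 0.0065)/√[(0.0327 × 0.9673 + 0.0065 × 0.9935)/2] = 0.19.

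| Severe, warfarin vs NOAC; R | a = 39.3%: factor, SD | a = 69.1%: factor, SD |
|---|---|---|
| 2% vs 0.2%; 3 | 0.978, 0.15 | 0.981, 0.14 |
| 3% vs 0.3%; 3 | 0.970, 0.18 | 0.974, 0.16 |
| 3% vs 0.3%; 4 | 0.951, 0.18 | 0.957, 0.16 |
| 5% vs 0.5%; 4 | 0.929, 0.21 | 0.941, 0.19 |

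The SD for the CKD flag is 0 throughout. At the other two shares the last row becomes 0.926 and 0.22 (edoxaban, 31.0%), and 0.921 and 0.23 (dabigatran, 16.8%). If the severe share within CKD is the same in both arms, e is equal and the factor is 1.

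**3. A wider set of assumptions.** Take a true HR of 0.75, severe disease in 0.5-4% of the cohort and other CKD in 4% at 1.5 times the hazard. Let NOAC use be 39.3% outside the severe group and 5-39.3% within it, with severe hazard 2-4 times that of other CKD. The flag-only PS then returns 0.643 to 0.750, and a PS with stage returns 0.750 every time. A middle case (1% severe, 10% of them on NOAC, hazard 2 times) gives 0.739.

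**4. Size against the plan's precision.** The plan's sample sizes follow the Schoenfeld formula. For apixaban at HR 0.75 it gives 33,397, against 33,340 stated. On the same basis, the HR that just reaches two-sided 5% significance is exp{-1.96/√[N·p·a(1 - a)]}:

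- Rivaroxaban: 89,124 × 8.1% = 7,219 events, boundary 0.951.
- Edoxaban: 42,924 × 8.5% = 3,649 events, boundary 0.932.
- Apixaban: 49,224 × 1.19% = 586 events, boundary 0.847.
- Dabigatran: 36,162 × 1.4% = 506 events, boundary 0.792.

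Only the most extreme row of step 2 passes a boundary: 0.941 for rivaroxaban and, narrowly, 0.926 for edoxaban. These boundaries ignore variance inflation from weighting.

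**The case against.** Four points on the other side have force.

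- **The PS is not blind to severity.** Some dialysis codings do score differently from stage 3, as step 1 shows. "Number of outpatient visits within the 6-month period prior to the index date", diuretics, heart failure, hypertension and diabetes may act as partial proxies. A reader might infer that the PS cannot separate these patients at all, and the documents do not support that. Nor do they show that the proxies suffice.
- **The bias is conditional.** It might be inferred that the hazard ratios are confounded and that every NOAC will look safer than warfarin. That needs drug choice to differ by stage within CKD, severe patients to go to warfarin, and bleeding risk to rise with stage. The documents quantify none of these, and the null case gives zero bias.
- **Weighting on the flag removes part of the effect.** A calculation treating everyone without severe disease as baseline risk, [1 + sN(R - 1)]/[1 + sW(R - 1)], gives 0.883-0.965 on the same severe-disease inputs. It overstates the bias, because the up-weighted stand-ins with moderate CKD are themselves at raised risk. The claim that the bias alone could produce significance holds only in the extreme cases of step 4.
- **The protocol acknowledges the problem in general.** Section 9.9 says "residual confounding from unmeasured or unaccounted confounders may be present" and that "laboratory data are unavailable for assessment due to inherent limitations of the HIRA database". It also promises: "Sensitivity analysis using the E-value will be conducted to quantify the impact of residual confounding". But stage and dialysis codes are recorded, and the SAP already reads them, so this confounder is measurable. The E-value is planned for apixaban only, is absent from the SAP, and measures how strong a confounder would need to be without checking balance.

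The other planned checks do not fill the gap. Trimming, PS as a covariate, PS deciles and SMR weights all reuse the same covariates. The stage 3-4 subgroup gives a contrast largely free of stage 5, but puts stage 5 and dialysis in its complement.

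**Conclusion.** The coding gap is certain. The PS has no stage 5 or dialysis term, stages 3 to 5 score identically on every renal covariate, and an imbalance in severe disease would not appear in Tables 13-16. The resulting bias is possible, not established. Under the assumptions of step 2 it is a factor of about 0.93-0.98 on the HR in favour of the NOAC (0.92 at the dabigatran share). Severe disease would have an SD of 0.14-0.21 (up to 0.23), which would breach the plan's own 0.1 limit unseen. It is zero if drug choice does not vary by stage within CKD, and proxies in the PS may reduce it. This should be corrected before Phase II because the data are in hand. It does not by itself invalidate the comparison.

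**What to change.** In SAP 8.4 and Protocol 9.3, replace the CKD flag in the PS and in Tables 13-16 with levels, each patient taking the highest that applies:

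1. none;
2. N18.1-N18.2, N18.9 or N19 only;
3. N18.3-N18.4;
4. N18.5, Z99.2 or Z49.

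Enter transplant (Z94.0) as a separate indicator, since nothing in the plan justifies pooling it with dialysis. Apply the SD < 0.1 criterion to each level.

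Add to SAP 10 and Table 20 one sensitivity analysis that excludes patients with N18.5, Z99.2 or Z49 from all four comparisons alike, so that the populations stay comparable, and report the number excluded.

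The cost is a wording change and minor extra coding. Every code needed is named in the SAP or falls under N18. The sensitivity analysis loses a small number of patients, and the main analysis loses none by design.

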Cancer surgeries	Specified in 'cancer-related surgery' of section 8.3.2
Benign surgeries	R4123-R4129, R4421, R4430, R3975
Cancer-related event (active cancer)	C00-C97 (excluding non-melanoma skin cancer, C44) with V code (V011, V027, V193, V194)
Kidney function change	
Chronic kidney disease	N18, N19
Acute kidney injury	N17
Liver function change	
Liver disease	B15-B19, K70-K77
Abnormal liver function	R94.5, R74.0

- **Phase II of the study**

- Major bleeding will be defined using primary or secondary diagnosis codes according to the ICD-10 diagnostic codes shown in below table and classified by site (intracranial, gastrointestinal [GI], all others).

Major bleeding	ICD-10 diagnosis code	Diagnostic definition
Intracranial hemorrhage	I60, I61, I62, I690, I691, I692, S064, S065, S066, S068	Diagnosis code + admission code + brain CT or MRI code

		* Brain CT or MRI: CT: HA441, HA451, HA461, HA471, HA851 MRI: HE101, HE102, HE135, HE201, HE202, HE235, HE301, HE302, HE401, HE402, HE501, HE502, HE535
GI bleeding	I850, I983, K2211, K226, K228, K250, K252, K254, K256, K260, K262, K264, K266, K270, K272, K274, K276, K280, K282, K284, K286, K290, K3181, K5521, K625, K920, K921, K922	Diagnosis code + admission code
Other bleeding	D62, H448, H3572, H356, H313, H210, H113, H052, H470, H431, I312, N020-N029, N421, N831, N857, N920, N923, N930, N938, N939, M250, R233, R040, R041, R042, R048, R049, T792, T810, N950, R310, R311, R318, R58, T455, Y442, D683	Diagnosis code + admission code

- The earliest date of diagnosis of the major bleeding event after the index date will be defined as the outcome occurrence date.
- Patients will be followed up from the index date to the occurrence of an outcome, treatment discontinuation (30-day grace period), switch to another anticoagulants, in-hospital death, or end of the study period (31 Dec 2019) whichever comes first.

Potential Confounder(s)

- Sociodemographic characteristics such as age, sex, and index year will be assessed at the index date.
- CCI [2] and HAS-BLED [3] scores will be measured within the 6-month period prior to the index date.

List of CCI	Score	ICD-10 codes
Cerebrovascular disease	1	G45, G46, H34, I60-I69
Congestive heart failure	1	I09.9, I11.0, I13.0, I13.2, I25.5, I42.0, I42.5-I42.9, I43, I50, P29.0
Chronic pulmonary disease	1	I27.8, I27.9, J40-J47, J60-J67, J68.4, J70.1, J70.3

Dementia	1	F00–F03, F05.1, G30, G31.1

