Note: PAC, parenteral anticoagulants; IQR, Interquartile range; std, standard deviation

Table 13. Pre- and post-weighted baseline characteristics of patients with venous thromboembolism who newly initiated apixaban and warfarin.

Characteristics	Pre-weighted			Post-weighted		
	Apixaban		Warfarin-based therapy	Apixaban	Warfarin-based therapy	aSD
	N=	(%)	N=	(%)	N=	(%)
Follow-up (days; median, IQR)						
Age (years; mean±std)						
Age group (years; n, %)						
18-40						
40-65						
≥65						
Sex (n, %)						
Male						
Female						
Health insurance type (n, %)						
National health insurance						
Medical aid						
Index year (n, %)						
2012						
2013						
2014						
2015						
2016						
2017						
2018						
2019						
CCI score (mean±std)						
HAS-BLED score (mean±std)						
Comorbidities (n, %)						
Antiphospholipid syndrome						
Asthma						
History of cancer						
COPD						
Chronic kidney disease						
Chronic liver disease						
Diabetes mellitus						
Fracture						

Heart failure
Hyperlipidemia
Hypertension
Ischemic heart disease
Myocardial infarction
Stroke
Trauma
Previous use of
medications (n, %)
Corticosteroids
NSAIDs
ACE inhibitors
Angiotensin II receptor
blockers
Aspirin
 β -blockers
Calcium-channel
blockers
SSRI
Proton pump inhibitors
Diuretics
Thiazides
Vasodilators
Estrogens
Cyclooxygenase-2
inhibitors
Outpatient visits
(mean \pm std)

Note: ACE, angiotensin-converting enzyme; aSD, absolute standardized difference; CCI, Charlson comorbidity index; COPD, chronic obstructive pulmonary disease; IQR, interquartile range; NSAIDs, nonsteroidal anti-inflammatory drugs; PAC, parenteral anticoagulants; SSRI, selective serotonin reuptake inhibitors; std, standard deviation

Table 14. Pre- and post-weighted baseline characteristics of patients with venous thromboembolism who newly initiated rivaroxaban and warfarin.

Characteristics	Pre-weighted			Post-weighted		
	Rivaroxaban	Warfarin-based therapy	aSD	Rivaroxaban	Warfarin-based therapy	aSD
	N= (%)	N= (%)		N= (%)	N= (%)	
Follow-up (days; median, IQR)						
Age (years; mean±std)						
Age group (years; n, %)						
18-40						
40-65						
≥65						
Sex (n, %)						
Male						
Female						
Health insurance type (n, %)						
National health insurance						
Medical aid						
Index year (n, %)						
2012						
2013						
2014						
2015						
2016						
2017						
2018						
2019						
CCI score (mean±std)						
HAS-BLED score (mean±std)						
Comorbidities (n, %)						

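### Cirrhosis without a coded complication looks like fatty liver or chronic hepatitis to every liver term in the propensity score, so confounding by liver severity may remain where the balance tables cannot show it

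*SAP*

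**What the plan says.** SAP section 8.4 (Potential Confounders) and Protocol section 9.3 list a single liver comorbidity, "Chronic liver disease (B18, B19, K70-K77"). Both also list two scores: "CCI [2] and HAS-BLED [3] scores will be measured within the 6-month period prior to the index date". Section 10 of the SAP feeds these baseline covariates into a logistic propensity model for each NOAC against warfarin.

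The SAP's score tables treat the liver as follows:
- CCI, mild liver disease, 1 point: "B18, K70.0-K70.3, K70.9, K71.3-K71.5, K71.7, K73, K74, K76.0, K76.2-K76.4, K76.8, K76.9, Z94.4".
- CCI, moderate or severe liver disease, 3 points: "I85.0, I85.9, I86.4, I98.2, K70.4, K71.1, K72.1, K72.9, K76.5, K76.6, K76.7".
- HAS-BLED, abnormal liver function, 1 point: "B15-B19, C22, D68.4, I98.2, I98.3, K70-K77, Z94.4".
- HAS-BLED, alcohol item, 1 point: "Alcoholism: E24.4, F10, G31.2, G62.1, G72.1, I42.6, K29.2, K70", among others.

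Tables 13-16 carry one chronic liver disease row and show the CCI only as a total ("CCI score (mean±std"). A covariate counts as balanced when its absolute standardized difference is below 0.1. On the outcome side, the GI bleeding list opens with "I850, I983, K2211, K226, K228"; by standard ICD-10 labels the first two are bleeding varices.

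**The concern.** A propensity score can balance only what its terms distinguish. If the liver terms give mild disease and cirrhosis the same values, weighting can balance the flag exactly and still leave cirrhosis unequal within it. The chronic liver disease row would then pass the 0.1 rule and say nothing about the part of liver disease most closely tied to variceal and other GI bleeding. The analyses at stake are the weighted hazard ratios in Table 17 and, above all, the GI rows of Table 18.

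The plan itself accepts liver disease as a bleeding risk, since it scores it in HAS-BLED. It grades the kidney more finely: HAS-BLED uses stage codes N18.3-N18.5, and CKD stage 3 or 4 is a planned subgroup. There is no liver counterpart.

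**Working it through.** **Step 1: score code profiles against the SAP's lists.** Code meanings are the standard ICD-10 labels.

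| Profile in the lookback | Flag | CCI liver points | HAS-BLED liver | HAS-BLED alcohol | HAS-BLED bleeding history |
|---|---|---|---|---|---|
| Fatty liver, K76.0 | 1 | 1 | 1 | 0 | 0 |
| Chronic hepatitis, B18 or K73 | 1 | 1 | 1 | 0 | 0 |
| Cirrhosis, K74.6 | 1 | 1 | 1 | 0 | 0 |
| Toxic liver disease with cirrhosis, K71.7 | 1 | 1 | 1 | 0 | 0 |
| Alcoholic fatty liver, K70.0 | 1 | 1 | 1 | 1 | 0 |
| Alcoholic cirrhosis, K70.3 | 1 | 1 | 1 | 1 | 0 |
| K74.6 with K76.6, I85.9, K72.9 or K76.7 | 1 | 3 (4 if both rows count) | 1 | 0 | 0 |
| K74.6 with I85.0 | 1 | 3 (4 if both rows count) | 1 | 0 | 1 |
| Non-bleeding varices, I85.9 only | 0 | 3 | 0 | 0 | 0 |

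Uncomplicated cirrhosis matches milder disease on every liver term. The alcohol point separates alcoholic from non-alcoholic disease, not cirrhosis from fatty liver.

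**Step 2: what the 3 CCI points are worth.** Only the total is tabulated. Diabetes with chronic complication (2) plus chronic pulmonary disease (1) also makes 3, so balance on the mean CCI does not establish balance on advanced liver disease.

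**Step 3: size, by illustration.** The documents give no prevalence, no cirrhosis share by arm and no bleeding rate ratio. Every input below is an assumption:
- flagged share of the cohort, f: 15-25%;
- cirrhosis among those flagged, c: 5-15%;
- odds ratio for NOAC rather than warfarin with cirrhosis: 0.33-0.5;
- bleeding rate ratio for cirrhosis, r: 3-5 overall and 8 for GI bleeding;
- bleeding rate ratio for milder liver disease, m: 1.1;
- NOAC share: 0.4 (the plan's apixaban figure is 39.3%).

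Let p1 and p0 be the probabilities of a NOAC with and without cirrhosis. They satisfy c·p1 + (1 − c)·p0 = 0.4 and the assumed odds ratio. The cirrhosis shares among flagged users are then cN = c·p1/0.4 and cW = c·(1 − p1)/0.6. With the flag balanced and a true HR of 1.00, the estimated HR is

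[(1 − f) + f((1 − cN)m + cN·r)] / [(1 − f) + f((1 − cW)m + cW·r)].

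- Large end (f = 0.25, c = 0.15, odds ratio 0.33): p1 = 0.2025, p0 = 0.4349, cN = 0.0759, cW = 0.1994. With r = 5: 1.0990/1.2194 = 0.90. With r = 8: 1.1560/1.3689 = 0.84.
- Small end (f = 0.15, c = 0.05, odds ratio 0.5): cN = 0.0320, cW = 0.0620. With r = 3: 1.0241/1.0327 = 0.99. With r = 8: 1.0481/1.0792 = 0.97.
- Middle (f = 0.20, c = 0.10, odds ratio 0.4): 0.97 with r = 3 and 0.95 with r = 5.
- Direction reversed (f = 0.25, c = 0.15, odds ratio 3): cN = 0.2354, cW = 0.0931. With r = 5: 1.2545/1.1158 = 1.12.
- Equal cirrhosis shares: exactly 1.00.

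**Step 4: what a cirrhosis balance row would read.** With pN = f·cN and pW = f·cW, the standardized difference is |pN − pW| divided by the square root of the mean of pN(1 − pN) and pW(1 − pW). At the large end this is |0.0190 − 0.0498|/0.1816 = 0.17; at the small end it is 0.05. Over f = 15, 20, 25%, c = 5, 10, 15% and odds ratios 0.33 and 0.5, it falls below 0.1 in 10 of 18 combinations, while the flag itself is perfectly balanced in all of them.

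**The case against.** A reader might infer that all cirrhosis is invisible to the score. The lists do not support that. Cirrhosis with coded varices, portal hypertension or liver failure earns 3 CCI points instead of 1. I85.0 and I98.3 also earn the HAS-BLED bleeding-history point, and the sensitivity analysis excluding patients with bleeding in the previous six months should remove varices that have already bled. The patients most exposed to variceal haemorrhage are therefore partly separated. That stands, although the separation depends on the complication being coded within six months and is diluted in the CCI total.

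A reader might also infer that the hazard ratios are confounded. Nothing in the documents says that cirrhosis influences the choice between a NOAC and warfarin, in either direction. New liver disease is listed among events that may precede a treatment change, but that concerns patients already on treatment.

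Three further points carry weight. Beta-blockers, diuretics, PPIs, bleeding history and the CCI are in the model and may absorb part of any imbalance; Step 3 gives them no credit. A rate ratio of 8 applied to all cirrhosis is generous. Other comorbidities, such as heart failure and diabetes, are pooled flags too, and Protocol 9.9 concedes residual confounding.

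These points limit the size but do not close the gap. The alternative propensity analyses (trimming, covariate adjustment, deciles, SMR weights) name no additional covariate. The E-value is in the Protocol only, is worded for apixaban, and does not reach SAP section 10.

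**Conclusion.** The point holds as a limit of the covariate set. The liver terms cannot distinguish uncomplicated cirrhosis from fatty liver or chronic hepatitis, they separate complicated disease only weakly, and no row of Tables 13-16 would show an imbalance in either. Confounding by liver severity is possible, not demonstrated.

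The 0.90-0.99 (overall) and 0.84-0.97 (GI) figures are upper-bound illustrations for the assumed ranges, because they ignore the other covariates. More extreme inputs would widen them: a flag prevalence of 30%, cirrhosis in 5% against 25% of those flagged, a rate ratio of 5 and no excess for milder disease give (1 + 0.30 × 0.05 × 4)/(1 + 0.30 × 0.25 × 4) = 1.06/1.30 = 0.82. Mid-range inputs give a shift of 3-5%. This does not invalidate Phase II. It is a plausible bias path that the planned check cannot see and that is cheap to close.

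**What to change.** In SAP 8.4 and Protocol 9.3 add two binary covariates over the same six-month lookback:
- cirrhosis: K70.3, K71.7, K74.3-K74.6;
- moderate or severe liver disease: the SAP's existing 3-point CCI list.

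Enter both in each propensity model as terms separate from the CCI sum, and give each a row with its standardized difference in Tables 13-16. The model terms matter more than the rows: Step 4 shows that a cirrhosis row alone could often read below 0.1 before any adjustment.

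The cost is a wording change in both documents, two model terms and two table rows. The codes are diagnoses in the claims database already being used, so no new data are needed, and no sample-size or alpha figure changes. The downside is slightly more variable weights.
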